19.5. Interim analyses and stopping rules

No formal interim analysis of efficacy will be performed however the IDMC will meet regularly (at least annually) to assess safety and tolerability and also to review the emerging data on ctDNA incidence to inform the anticipated overall size of the therapeutic trial (i.e. to ensure processes in place for sufficient drug supply etc.) and to determine the relevant success criteria for the above A'Hern design required.

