19.1.2. Therapeutic component

Under the original randomised study design (prior to protocol v6.0), those patients allocated via randomisation to observation provide a reference control rather than a formal randomised comparator group. The statistical considerations underpinning the therapeutic intervention evaluation are those of a single group trial with patients treated with pembrolizumab in both the randomised and non-randomised

trial components combined. The original design hypothesised frequencies of ctDNA+ and allocation to pembrolizumab as per the text and table outlined below. The revision in the design to close the randomised component has the potential to increase the number of patients commencing pembrolizumab. No redefinition of the criteria have been undertaken since the success criteria are determined by the number starting treatment and not the overall proportion available to receive treatment.

The rate of ctDNA positivity is prone to stochastic effects, and as such a range of effect sizes is presented. All patients in the screening cohort who are observed to have a positive ctDNA will be entered into the therapeutic component, therefore the eventual number entering that phase will only be defined as the trial progresses. The most likely incidence, on which the primary calculations were made, is for a 30% positivity rate during the first 12 months. Calculations use an A'Hern single-stage design within pembrolizumab treated patients, alpha=0.1, power=90%, unacceptable ctDNA clearance rate p0 (of 0.3) and minimum required level of efficacy p1 of approximately 0.5. The number of clearances to conclude the required level of success and width of the 95% confidence interval which could be detected around a proportion with ctDNA clearance of approximately 0.5 are given for each hypothesised rate of ctDNA positivity.

Rate of ctDNA positivity	No. ctDNA positive (of 150 in ctDNA surveillance phase)	No. randomised to receive pembrolizumab	р0	р1	No. successes required	Width of 95% confidence interval detectable around proportion of 0.5
45%	68	45	0.30	0.49	18	+/- 0.14
30%	45	30	0.30	0.54	13	+/- 0.17
24%	36	24	0.30	0.57	10	+/- 0.19

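### Sections 19.1.2 and 19.5 give different inputs for the pembrolizumab success threshold; the table's incidence columns are out of date, and its 24-patient row does not hold alpha at 10%

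*Protocol*

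**What the plan says.** Protocol section 19.1.2 sets the therapeutic test: "Calculations use an A'Hern single-stage design within pembrolizumab treated patients, alpha=0.1, power=90" per cent, with an unacceptable clearance rate of 0.30 and a "minimum required level of efficacy p1 of approximately 0.5". Required successes "are given for each hypothesised rate of ctDNA positivity". The table has three rows:

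| ctDNA positivity | Positive of 150 | Randomised to pembrolizumab | p1 | Successes required |
|---|---|---|---|---|
| 45% | 68 | 45 | 0.49 | 18 |
| 30% | 45 | 30 | 0.54 | 13 |
| 24% | 36 | 24 | 0.57 | 10 |

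The same section deals with the closure of randomisation in v6.0. It accepts that more patients may now start pembrolizumab, and adds: "No redefinition of the criteria have been undertaken since the success criteria are determined by the number starting treatment", as opposed to the overall proportion available for treatment.

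Section 19.5 plans no formal interim efficacy analysis. It has the IDMC review safety, tolerability and emerging ctDNA incidence. The incidence review serves to anticipate the size of the therapeutic trial and "to determine the relevant success criteria for the above A'Hern design required".

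Section 19.2 states that from v6.0 every patient with a positive result is allocated to pembrolizumab; before that, allocation was 2:1. Section 19.4 makes the primary-endpoint analysis intention-to-treat, including patients who decline treatment or are ineligible for reasons other than recurrence. Its per-protocol sensitivity analysis is limited to patients who start.

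**The concern.** One integer decides whether pembrolizumab is declared active, and the protocol does not say unambiguously how that integer is obtained. Section 19.5 starts from incidence and section 19.1.2 from the number starting treatment. The only printed bridge between the two is the table, and its middle column is two thirds of the positives, the allocation that no longer applies. A given incidence therefore no longer identifies a row.

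Reading by number treated avoids that difficulty but leaves two others. Thresholds are printed for three values of n only, although 19.1.2 expects n to change and 19.1.1 lets the screening cohort grow or shrink. One of the three printed thresholds also misses the stated alpha. A threshold that is too low makes it easier to declare a drug with 30% clearance a success.

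**Working it through.** **Inputs.** p0 = 0.30, alpha = 0.10, power 90%, and the table rows, all from 19.1.2; the allocation ratios are from 19.2. The A'Hern test is one-sided. With X the number of clearances among n patients:

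- type I error = P(X ≥ r | n, 0.30)
- power = P(X ≥ r | n, p1)
- r(n) = the smallest r with P(X ≥ r | n, 0.30) ≤ 0.10

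All are exact binomial tails.

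**Step 1: reproduce the table, read by number treated.**

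| n | Printed r | Type I error | Power at the row's p1 | r(n) |
|---|---|---|---|---|
| 45 | 18 | 9.9% | 91.3% | 18 |
| 30 | 13 | 8.4% | 91.2% | 13 |
| 24 | 10 | 15.3% | 95.7% | 11 |

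The first two rows reproduce. The third does not: 11 of 24 gives 7.4% with power 90.4% at p1 = 0.57, so 11 meets both stated limits. Reading the column as more than r successes does not rescue the table. It repairs the 24 row but drops power to 83.9% for n = 30 (14 needed) and 85.5% for n = 45 (19 needed).

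**Step 2: the link from incidence to n.** 150 × 0.45 × 2/3 = 45; 150 × 0.30 × 2/3 = 30; 150 × 0.24 × 2/3 = 24. The number treated is the 2:1 share of the positives. The analysis pools patients treated under 2:1 with patients treated under full allocation, so at 30% incidence the number allocated lies between 30 and 45. The number who start can be lower, because patients with macroscopic disease, ineligible patients and refusers do not start (sections 3.2.1 and 9.3). The documents do not give the actual n.

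**Step 3: what would follow if the threshold were nevertheless read by incidence.** Hold r = 13 (the 30% row) and vary the number treated:

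| n | 26 | 28 | 30 | 33 | 36 | 40 | 45 |
|---|---|---|---|---|---|---|---|
| Type I error | 2.6% | 4.9% | 8.4% | 16% | 26% | 42% | 62% |

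The error falls as well as rises. The 62% needs all 45 positives to start. The matching extreme for the 45% row (18 of 68) is 78%.

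**Step 4: values of n between and above the rows.** The fixed inputs give r(36) = 15 (9.2%), r(40) = 17 (6.3%; 16 would give 11.5%) and r(68) = 26 (9.1%). None of these is printed.

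**The case against.** The best defence is that 19.1.2 already settles the matter. It was revised for this amendment, says that the number starting treatment governs, and fixes the method, p0 and alpha. Given n, the threshold is then a single determined integer. Section 19.5 can be read consistently with this: incidence informs size, and size gives the threshold. Missing values of r(n) are tabulation that an analysis plan can carry.

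Most of that stands. A reader might infer from 19.5 and the stale columns that the trial's type I error is 62% or 78%. The documents do not support this. Those figures need the incidence reading that 19.1.2 rejects, and also need every positive patient to start. Section 1.2.1 reports more overt metastatic disease than predicted, so starters could number fewer than 30, where 13 is conservative.

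A reader might also infer that the IDMC could tune the threshold to observed clearance. That is not supported either. No interim efficacy analysis is planned, the inputs listed for the IDMC are safety, tolerability and incidence, and 1.2.1 does not cite pembrolizumab clearance results as a reason for v6.0.

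The defence does not reach three things. Section 19.5 still assigns the IDMC a choice that should be automatic. The 24-patient row is wrong on the reading that 19.1.2 itself prescribes. And n is unsettled, because 19.1.2 counts starters while the primary analysis in 19.4 includes non-starters.

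**Conclusion.** The point holds as a conflict between 19.1.2 and 19.5 about what sets the trial's one decision threshold, together with a table that is partly superseded, sparse and wrong in one row. Read by number treated, 13 of 30 and 18 of 45 keep type I error below 10%. The definite numerical error is 10 of 24, which gives 15.3% against a stated 10%; 11 are needed. The drift in step 3 is conditional on reading by incidence and depends on an n that the documents do not give. It shows why the wording should be closed off, and is not an estimate of the trial's error rate. All figures assume a one-sided exact binomial test at p0 = 0.30.

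**What to change.** In 19.1.2 and 19.5, state one rule: success if X ≥ r(n), where r(n) is the smallest r with P(X ≥ r | n, 0.30) ≤ 0.10. Print the look-up for n = 20 to 68:

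| n | r(n) | n | r(n) | n | r(n) |
|---|---|---|---|---|---|
| 20–22 | 10 | 37–39 | 16 | 54–56 | 22 |
| 23–25 | 11 | 40–42 | 17 | 57–59 | 23 |
| 26–27 | 12 | 43–45 | 18 | 60–62 | 24 |
| 28–30 | 13 | 46–47 | 19 | 63–65 | 25 |
| 31–33 | 14 | 48–50 | 20 | 66–68 | 26 |
| 34–36 | 15 | 51–53 | 21 | | |

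This keeps 13 and 18 and changes the 24-patient entry to 11. Also:

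- Label the positivity and number-positive columns as the pre-v6.0 planning basis.
- Delete the IDMC's task of determining the success criteria. It keeps incidence for drug supply and cohort size.
- State which set defines n and X, reconciling the starters in 19.1.2 with the intention-to-treat set in 19.4, so that both come from the same patients.

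The cost is a few sentences and one table in an amendment. No patients, samples or data change. The choice of analysis set needs a decision by the trial team, made without knowledge of clearance results.

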20. TRIAL MANAGEMENT

20.1. Trial Management Group (TMG)

A Trial Management Group (TMG) will be set up and will include the Chief Investigator, ICR-CTSU Scientific Lead, Co-investigators and identified collaborators, the Trial Statistician and Trial Manager. Principal Investigators and key trial personnel will be invited to join the TMG as appropriate to ensure representation from a range of sites and professional groups. Where possible, membership will include a lay/consumer representative. The TMG will meet at regular intervals, and at least annually. Notwithstanding the legal obligations of the Sponsor and Chief Investigator, the TMG have operational responsibility for the conduct of the trial. The Committee's terms of reference, roles and responsibilities will be defined in a charter issued by ICR-CTSU.

20.2. Trial Steering Committee (TSC)

The trial will be monitored by the generic ICR-CTSU Breast Systemic Therapy Trials Steering Committee (TSC). The TSC will meet at regular intervals, and at least annually. The TSC will provide expert independent oversight of the trial on behalf of the Sponsor and funder. The Committee's terms of reference, roles and responsibilities will be defined in charter issued by ICR-CTSU and based on MRC Good Clinical Practice (MRC GCP).

20.3. Independent Data Monitoring Committee (IDMC)

An Independent Data Monitoring Committee (IDMC) will be set up to monitor the progress of the trial and will comprise a Chairman and at least two further members with clinical or statistical expertise (at least one member must be a statistician). Membership of the IDMC will be proposed by the TMG and approved by the TSC.

The IDMC will meet in confidence at regular intervals, and at least annually. A summary of findings and any recommendations will be produced following each meeting. This summary will be submitted to the TMG and TSC, and if required, the main REC and the MHRA.

The IDMC will reserve the right to release any data on outcomes or side-effects through the TSC to the TMG (and if appropriate to participants) if it determines at any stage that the combined evidence from this and other studies justifies it.

The Committee's terms of reference, roles and responsibilities will be defined in a charter issued by ICR-CTSU.

21. RESEARCH GOVERNANCE

21.1. Sponsor responsibilities

The Sponsor of the c-TRAK TN trial is the Institute of Cancer Research (ICR).

21.2. Participating site responsibilities

Responsibilities delegated to participating sites are defined in an agreement between the Sponsor and the individual site.

21.3. Merck Sharp & Dohme responsibilities

Merck Sharp & Dohme (MSD) on behalf of the Sponsor will manufacture, package, and label trial drug in accordance with Good Manufacturing Practice and all applicable local legislation. Responsibilities are defined in an agreement between MSD and the Sponsor.

21.4. Mawdsleys responsibilities

Mawdsleys on behalf of the Sponsor will distribute the trial drug to sites in accordance with Good Manufacturing Practice and all applicable local legislation. Responsibilities are defined in an agreement between Mawdsleys and the Sponsor.

22. TRIAL ADMINISTRATION & LOGISTICS

22.1. Site activation

Before recruitment can commence at a site, the site agreement must have been signed by all required signatories, the required trial documentation (as specified by ICR-CTSU) must be in place and a site initiation must have taken place. Site initiation may be by teleconference or by on site visit if requested by the Principal Investigator or if deemed appropriate by ICR-CTSU. ICR-CTSU will provide the final confirmation that recruitment can commence at a site.

22.2. Data acquisition

Electronic Case Report Forms (eCRFs) will be used for the collection of trial data from source data. ICR-CTSU will provide guidance to sites to aid the completion of the eCRFs. The Trial Management Group reserves the right to amend or add to the eCRF template as appropriate. Such changes do not constitute a protocol amendment, and revised or additional forms should be used by sites in accordance with the guidelines provided by ICR-CTSU.

22.3. Central data monitoring

Once data has been entered on the eCRF by the site personnel, ICR-CTSU will review it for compliance with the protocol, and for inconsistent or missing data. Should any missing data or data anomalies be found, queries will be raised for resolution by the site.

Any systematic inconsistencies identified through central data monitoring may trigger an on-site monitoring visit.

22.4. On-site monitoring

If a monitoring visit is required, ICR-CTSU will contact the site to arrange the visit. Once a date has been confirmed, the site should ensure that full patient notes of participants selected for source data verification are available for monitoring.

ICR-CTSU staff conducting on-site monitoring will review essential documentation and carry out source data verification to confirm compliance with the protocol. If any problems are detected during the course of the monitoring visit, ICR-CTSU will work with the Principal Investigator or delegated individual to resolve issues and determine appropriate action.

22.5. Completion of the trial and definition of Trial End Date

The trial end date is deemed to be the date of last data capture.

22.6. Archiving

Essential trial documents should be retained according to local policy and for a sufficient period for possible inspection by the regulatory authorities (at least 5 years after the date of last data capture). Documents should be securely stored and access restricted to authorised personnel.

23. PATIENT PROTECTION AND ETHICAL CONSIDERATIONS

23.1. Trial approvals

This trial has been formally assessed for risk by the Sponsor.

ICR-CTSU, on behalf of the Sponsor, will ensure that the trial has received ethics approval from a research ethics committee for multi-centre trials, regulatory approval from the MHRA and the relevant NHS permissions. Before recruiting patients, the Principal Investigator at each site is responsible for gaining local approvals.

23.2. Trial conduct

This trial will be conducted according to the approved protocol and its amendments, supplementary guidance and manuals supplied by the Sponsor and in accordance with The Medicines for Human Use (Clinical Trials) Regulations 2004 as amended, the Research Governance Framework for Health and Social Care and the principles of GCP.

23.3. Informed consent

Patients should be asked to sign the current ethics approved c-TRAK TN consent form at trial entry and prior to starting treatment after receiving both verbal and written information about the trial, having been given sufficient time to consider this information. All consent forms must be countersigned by the Principal Investigator or a designated individual. A signature log of delegated responsibilities, listing the designated individuals and the circumstances under which they may countersign consent forms, must be maintained at the participating site. This log, together with original copies of all signed patient consent forms, should be retained in the Site Investigator File and must be available for inspection. The current ethics approved c-TRAK TN patient information sheets should be provided in addition to any standard patient information sheets that are provided by the site and used in routine practice.

23.4. Patient confidentiality

Patients will be asked to consent to their full name being collected at trial entry in addition to their date of birth, hospital number, postcode and NHS number or equivalent to allow linkage with routinely collected NHS data and ensure accuracy in handling biological samples.

Each investigator should keep a separate log of all participants' Registration Numbers, Trial IDs, names, addresses and hospital numbers. The investigator must retain trial documents (e.g. participants' written consent forms) in strict confidence. The investigator must ensure the patients' confidentiality is maintained at all times.

Representatives of ICR-CTSU and the regulatory authorities will require access to patients' hospital notes for quality assurance purposes. ICR-CTSU will maintain the confidentiality of participants at all times and will not reproduce or disclose any information by which participants could be identified.

23.5. Data protection

ICR-CTSU will comply with all applicable data protection laws.

23.6. Insurance and liability

Indemnity to meet the potential legal liability of investigators participating in this trial is provided by the usual NHS indemnity arrangements.

24. FINANCIAL MATTERS

This trial is investigator designed and led, has been endorsed by Clinical Research Committee (CRC) of Cancer Research UK, and meets the criteria for R&D support as outlined in the Statement of Partnership on Non-Commercial R&D in the NHS in England.

The trial is part of the National Institute for Health Research Clinical Research Network (NIHR CRN) portfolio by virtue of its endorsement by CRC. NIHR CRN resources should therefore be made available for the trial to cover UK specific research costs.

The Sponsor has received Investigator Initiated Research grants (IIR) from Merck Sharp & Dohme and ICR NIHR Biomedical Research Centre for the conduct of this trial.

25. PUBLICATION POLICY

The main trial results will be published in a peer-reviewed journal, on behalf of all collaborators. The manuscript will be prepared by a writing group, consisting of members of the TMG. Participating clinicians may be selected to join the writing group on the basis of intellectual and time input. All participating clinicians will be acknowledged in the publication.

Patient participation will be acknowledged in any publication resulting from the c-TRAK TN trial. Results of the trial will be sent to treating clinicians to relay to patients who participated in the trial.

Any presentations and publications relating to the trial must be authorised by the TMG. Authorship of any secondary publications e.g. those relating to sub-studies, will reflect intellectual and time input into these studies.

No investigator may present or attempt to publish data relating to the c-TRAK TN trial without prior permission from the TMG.

26. ASSOCIATED STUDIES

26.1. Translational studies

26.1.1. **PDL1**

Archival tissue may be used to assess PD-L1 assessment by IHC (subject to funding availability). PD-L1 can be shed from tumour and released into the blood, which would be a less invasive component to measure PD-L1 protein biomarker. Analyses may include exploratory analysis of time from ctDNA detection and disease recurrence according to tumour PDL1 expression and prediction of sustained ctDNA clearance on pembrolizumab by PD-L1 expression.

26.1.2. Nucleic acid extractions and analyses

Nucleic acids including DNA and RNA will be extracted from tissue samples, and DNA will be extracted from normal buffy coat and plasma. DNA samples will be subjected to digital PCR or sequencing analysis or other molecular techniques to identify mutations relevant to cancer biology.

Exploratory analyses may include identification of biomarkers that predict sustained ctDNA clearance on pembrolizumab, and predictor relapse and ctDNA detection.

26.1.3. **Protein analysis**

Tissue sections from the trial will be analysed by immunohistochemistry, immunofluorescence, or other techniques for analysis of proteins. Tissue samples may be processed for analysis of proteins using alternative techniques.

Exploratory analyses may include identification of biomarkers that predict sustained ctDNA clearance on pembrolizumab, and predictor relapse and ctDNA detection.

26.1.4. Assessment of intra-tumoural heterogeneity and clonality

Exploratory assessment will be made on whether a targetable mutation is apparently clonal (likely present in all cancer cells in the tumour) or sub-clonal (present in only a subset of cancer cells in the body). Evidence of sub-clonality may include discordance in the mutation between ctDNA surveillance blood sample and tissue biopsy, or evidence that the mutation has reduced allele frequency compared to other mutations present in the ctDNA.

26.1.5. Assessment of isolated PBMC

Blood samples for PBMC isolation will be collected from patients at designated (geographically determined) PBMC sites. These samples will be used for exploratory research on predictors of sustained ctDNA clearance on pembrolizumab. PBMC will be isolated from the blood tests, and live PBMC cells frozen in the central laboratory. PBMC will be grown to isolate cytotoxic T cells, and establish if patient cytotoxic T cells can recognise tissue mutations. PBMC isolated on treatment (cycle 3) will be used to explore whether cytotoxic T cells expand on pembrolizumab therapy, and whether expansion of cytotoxic T cells predicts for sustained ctDNA clearance.

- 29. Aboudaram, A., et al., *Concurrent radiotherapy for patients with metastatic melanoma and receiving anti-programmed-death 1 therapy: a safe and effective combination.* Melanoma Res, 2017. **27**(5): p. 485-491.
- 30. Rustin, G.J., et al., *Early versus delayed treatment of relapsed ovarian cancer (MRC OV05/EORTC 55955): a randomised trial.* Lancet, 2010. **376**(9747): p. 1155-63.

A1. ECOG performance status

Grade	Performance Status
0	Able to carry out all normal activity without restriction.
1	Restricted in physically strenuous activity but ambulatory and able to carry out light work.
2	Ambulatory and capable of all self-care but unable to carry out any work; up and about more than 50% of waking hours.
3	Capable of only limited self-care; confined to bed or chair more than 50% of waking hours.
4	Completely disabled; cannot carry on any self-care; totally confined to bed or chair.

A2. Contraception

Male patients will be considered to be of non-reproductive potential if they have azoospermia (whether due to having had a vasectomy or due to an underlying medical condition).

Female patient will be considered of non-reproductive potential if:

 They are postmenopausal (defined as at least 12 months with no menses without an alternative medical cause; in women <45 years of age a high follicle stimulating hormone (FSH) level in the postmenopausal range may be used to confirm a post-menopausal state in women not using hormonal contraception or hormonal replacement therapy. In the absence of 12 months of amenorrhea, a single FSH measurement is insufficient);

OR

2. Have had a hysterectomy and/or bilateral oophorectomy, bilateral salpingectomy or bilateral tubal ligation/occlusion, at least 6 weeks prior to screening;

OR

3. Have a congenital or acquired condition that prevents childbearing.

Female and male patients of reproductive potential must agree to avoid becoming pregnant or impregnating a partner, respectively, from trial registration for the ctDNA surveillance phase of the study and, if allocated to pembrolizumab treatment, whilst receiving trial drug and for 120 days after the last dose of trial drug by complying with one of the following:

- 1. Practice abstinence⁺ from heterosexual activity;
 - OR
- 2. Use (or have their partner use) acceptable contraception during heterosexual activity.

Acceptable methods of contraception are:

- Single method (one of the following is acceptable):
 - o intrauterine device (IUD)
 - vasectomy of a female patient's male partner
 - o contraceptive rod implanted into the skin
- Combination method (requires use of two of the following):
 - o diaphragm with spermicide (cannot be used in conjunction with cervical cap/spermicide)
 - cervical cap with spermicide (nulliparous women only)
 - contraceptive sponge (nulliparous women only)
 - male condom or female condom (cannot be used together)
 - hormonal contraceptive: oral contraceptive pill (oestrogen/progestin pill or progestin-only pill), contraceptive skin patch, vaginal contraceptive ring, or subcutaneous contraceptive injection

⁺Abstinence (relative to heterosexual activity) can be used as the sole method of contraception if it is consistently employed as the patient's preferred and usual lifestyle. Periodic abstinence (e.g., calendar, ovulation, sympto-thermal, post-ovulation methods, etc.) and withdrawal are not acceptable methods of contraception.

Patients should be informed that taking the trial medication may involve unknown risks to the foetus (unborn baby) if pregnancy were to occur during the trial. In order to participate in the trial patients of childbearing potential must adhere to the contraception requirement (described above) from registration, throughout ctDNA surveillance and, if allocated to receive pembrolizumab treatment, whilst receiving trial medication up to 120 days after the last dose of trial therapy. If there is any question that a patient of childbearing potential will not reliably comply with the requirements for contraception, that patient should not be entered into the trial.

A3. Pembrolizumab use in pregnancy and nursing women

Use in pregnancy

If a patient inadvertently becomes pregnant while on treatment with pembrolizumab, the patient will immediately be discontinued from trial treatment. The site will contact the patient at least monthly and document the patient's status until the pregnancy has been completed or terminated. The outcome of the pregnancy will be reported to the Chief Investigator or TMG without delay.

Use in nursing women

It is unknown whether pembrolizumab is excreted in human milk. Since many drugs are excreted in human milk, and because of the potential for serious adverse reactions in the nursing infant, patients who are breast-feeding are not eligible for enrollment.

A4. GLOSSARY

AE	Adverse Event
ALT	Alanine Aminotransferase
ANC	Absolute Neutrophil Count
AST	Aspartate Aminotransferase
AUC	Area Under Curve
CI	Chief Investigator
CIS	Carcinoma In Situ
CRF	Case Report Form
ctDNA	Circulating Tumour DNA
DCF	Data Capture Form
DFS	Disease Free Survival
eCRF	Electronic Case Report Form
EORTC	European Organisation for Research and Treatment of Cancer
FBC	Full Blood Count
G-CSF	Growth Colony-Stimulating Factors
GFR	Glomerular Filtration Rate
HR	Hazard Ratio
IB	Investigator's Brochure
ICR	The Institute Of Cancer Research
ICR-CTSU	The Institute Of Cancer Research Clinical Trials and Statistics Unit
IDMC	Independent Data Monitoring Committee
LFT	Liver Function Test
MDT	Multi-disciplinary team
NCI CTCAE	National Cancer Institute Common Terminology Criteria for Adverse Events
PI	Principal Investigator
PIS	Patient Information Sheet
PBMC	Peripheral Blood Mononuclear Cell
QoL	Quality of Life
R&D	Research and Development
RCT	Randomised Controlled Trial
SAE	Serious Adverse Event
SAR	Serious Adverse Reaction

c-TRAK TN Protocol

SMPC	Summary of Product Characteristics
SUSAR	Suspected Unexpected Serious Adverse Reaction
TMG	Trial Management Group
TSC	Trial Steering Committee
U+E	Urea & Electrolytes
ULN	Upper Limit of Normal
WBC	White Blood Cell
WHO	World Health Organisation

This protocol is a controlled document and should not be copied, distributed or reproduced without the written permission of the ICR-CTSU
